## Funder

This research project is sponsored by Imperial College London. There is no commercial partner involved in this Research Study. There is no conflict of interest declared in the study protocol.

This protocol describes the '***Intra-operative ultrasound guided laparoscopic ovarian cystectomy (UGLOC) as a method of fertility preservation in the management of benign ovarian cysts: Randomised Controlled Trial***' study and provides information about procedures for entering participants. Every care was taken in its drafting, but corrections or amendments may be necessary. These will be circulated to investigators in the study. Problems relating to this study should be referred, in the first instance, to the Chief Investigator.

This study will adhere to the principles outlined in the UK Policy Frame Work for Health and Social Care Research. It will be conducted in compliance with the protocol, the Data Protection Act 2018 and other regulatory requirements as appropriate.

## **GLOSSARY OF ABBREVIATIONS**

## KEYWORDS

- Fertility Preservation Surgery
- Intra-operative Ultrasound
- Benign Ovarian Cyst
- Anti-Mullerian Hormone

## STUDY SUMMARY

**TITLE**

Intra-operative ultrasound guided laparoscopic ovarian cystectomy (UGLOC) as a method of fertility preservation in the management of benign ovarian cysts:  
Randomised Controlled Trial

**DESIGN**

A multi-centre prospective cohort non-blinded randomised controlled trial

**AIMS**

To assess whether intra-operative ultrasound is a significant method of fertility preservation surgery in the treatment of women of reproductive age with benign ovarian pathology.

**OUTCOME  
MEASURES**

Primary Outcome: Anti-Mullerian hormone (AMH) and Antral Follicle Count (AFC) measured at 3 and 6 months post-operatively

Secondary Outcome: Surgical outcomes will be measured including:

- Duration of hospital stay (days)
- Duration of surgery (minutes)
- Presence of intra-operative cyst rupture (Yes/No)

**POPULATION**

Females aged 18 -50 years old with a benign ovarian cyst requiring surgical management of pathology.

Women with: Cyst size  $\geq 3\text{cm}$ ;  $\leq 10\text{cm}$

**ELIGIBILITY**

IOTA B features of an ovarian cyst:

Unilocular, solid components: largest diameter  $\leq 7\text{mm}$ , acoustic shadows, no blood flow, smooth multilocular cyst: largest diameter  $\leq 100\text{cm}$ .

**DURATION**

3 years

## REFERENCE DIAGRAM

See Appendices 1-3

## 1.0 INTRODUCTION

### 1.1 BACKGROUND

Over the last few decades, advancements within the field of reproductive medicine have facilitated the rapidly emerging sub-specialty in gynaecology known as fertility preservation. Fertility preservation includes various methods to preserve reproductive tissue or gametes such as medical, surgical or laboratory techniques, thus empowering women to preserve their fecundity with a view to achieving pregnancy at a later date. Cancer is the second leading cause of death in women of reproductive age (<45 years old), therefore focus within the specialty has predominantly concerned female cancer patients. This is because a number of treatment options for cancer including chemotherapy or radiotherapy are gonadotoxic in nature rendering women infertile. With survival rates of cancer in women of reproductive age as high as 70% in adults, a number of women are subsequently faced, albeit, with either cure or remission of disease, but also the burden of infertility. The inability to bear children is associated with psychological distress and sequelae, therefore fertility preservation is deemed an important quality of life matter.

Consequently, there has been an increasing demand for less radical surgical management of gynaecological cancers, with a shift towards conservative methods in order to preserve the reproductive organs. In appropriately selected women, this enables the opportunity to balance the risks of recurrence from disease with less radical surgery, whilst reserving the ability to conceive in the future. For example, previous management of borderline ovarian tumours, included radical debulking surgery which required bilateral salpingo-oophorectomy. Fertility sparing surgery (FSS), which now includes unilateral salpingo-oophorectomy (USO) or ovarian cystectomy is considered the mainstay treatment in women with early-stage disease, non-invasive implants or for those who wish to conceive. Evidence suggests that the 5-year overall survival following FSS is similar to that of debulking surgery. However, the risk of relapse when ovarian cystectomy and USO are performed is increases from 13% to about 6%. In the context of BOT, FSS is deemed safe when concurrent surveillance monitoring for detection of recurrence is carried out, allowing women the opportunity to conceive during interval monitoring of disease.

There are many causes of infertility in women including benign pathology such as endometriosis or ovarian cysts. Infertility is caused either by the underlying pathology itself, or indirectly associated with the surgical intervention required to treat. The latter is attributed to the fact that ovarian surgery, despite minimally invasive techniques, results in the resection of a number of healthy ovarian follicles and tissue. Anti-Mullerian Hormone (AMH), a reliable marker of ovarian reserve, has been observed to be reduced post-operatively following surgery for endometriosis. The lifetime risk of a women

undergoing surgery for the presence of benign ovarian pathology is 5-10%. It is understandable therefore, why an increasing demand for the implementation of fertility sparing surgical techniques for women with benign pathology is also prevalent. Such demand is exacerbated further by the fact that the age of motherhood has increased over the last few decades. Increasing age however, is associated with poorer oocyte quality and yield, therefore increases the risk of involuntary childlessness as a direct consequence of age related fertility decline. If women delay attempting pregnancy to a later age, in addition to the risks of surgically induced impairment of ovarian tissue, overall chances of achieving pregnancy in the future maybe significantly reduced. It is imperative therefore, that fertility sparing techniques are implemented where possible in women of reproductive age, in order to optimize the chances of future successful conception.

## 1.2 RATIONALE FOR CURRENT STUDY

The use of intraoperative ultrasound has been widely implemented amongst other specialties. However, within gynaecological surgery, it is not as commonly recognized, despite evidence that it can be used as an adjunct to improving minimally invasive surgical techniques. This is primarily due to the improved visualization of the operative field which can assist more technically difficult surgical procedures, thus minimizing intraoperative complications. The application of ultrasound guidance within gynaecological procedures have included predominantly ovarian cyst aspiration, in vitro fertilization and removal or insertion of intra uterine devices. Although pre-operative imaging provides procedural planning, it cannot compare to the information gained from real time imaging. For example, in previous studies, intraoperative ultrasound detected more myomas during myomectomy than pre-operative transvaginal imaging. Furthermore, it provides the potential to assess lesion margins, ensuring resection of pathology is complete with negligible damage to surrounding healthy tissues. This is consistent with a recent systematic review, which also demonstrated that albeit a novel technique, amongst various case series, pathology can be safely resected without incurring injury to healthy reproductive tissue. Therefore, intraoperative ultrasound has the potential to improve surgical accuracy, reduce complications and improve patient safety. The application of intraoperative ultrasound as an adjunct to fertility sparing surgery has not been widely researched, with only a few case series reporting surgical outcomes on patients undergoing treatment for pre-malignant or malignant pathology. The aim of this study therefore, is to determine the efficacy of this surgical technique in the management of benign pathology including the surgical resection of ovarian cysts.

## 1.3 RESEARCH QUESTION

The primary objective of this study is to determine the efficacy of intraoperative ultrasound-guided ovarian cystectomy (UGLOC) for the management of benign ovarian cysts as an adjunct of fertility sparing surgery. This will be determined through assessment of post-operative AMH and AFC, which are both reliable measures of ovarian reserve. The secondary objective is to determine the surgical outcomes in women who have undergone intraoperative ultrasound guided ovarian cystectomy and compare this to the control group.

## 2.0 STUDY OBJECTIVES

### *Primary objectives*

To determine the efficacy of intraoperative ultrasound guided ovarian cystectomy as an additional method of fertility preservation.

### *Secondary objectives*

To determine the surgical outcomes in participants who have undergone intraoperative ultrasound guided ovarian cystectomy and compare to the control group.

## 3.0 STUDY DESIGN

This will be a multi-centre prospective cohort study carried out as a non-blinded randomised controlled trial. Participants will be allocated to either a control group of laparoscopic ovarian cystectomy performed without ultrasound guidance, or to the experimental ultrasound guided laparoscopic ovarian cystectomy (UGLOC) group. All surgeons operating and participants recruited to the study will be aware of which group they have been allocated to from the beginning of the study. The investigators aim for equal sample sizes in both groups (see power calculation below).

Participants will include all women of reproductive age diagnosed with a benign ovarian cyst requiring surgical management. The duration of the study from recruitment to end of data collection will be approximately 3 years (01/10/21-01/10/24).

Women referred to the outpatient gynecology clinic with a suspected ovarian cyst will be asked about their clinical history and undergo a pelvic transvaginal ultrasound scan (2D and 3D ultrasonography) as part of routine clinical care. If an ovarian cyst is seen on ultrasound, it will be assessed according to local protocols based on simple descriptors and international ovarian tumor analysis (IOTA) simple rules. Depending on the severity of symptoms, nature of the cyst and fulfilment of the inclusion criteria and if the woman is suitable for surgical management, she will then be invited to participate in the study.

Participants will be recruited from various general gynaecology clinics as well as specialist clinics including: ovarian cyst, the IOTA and rapid access clinics across Imperial and University College London Hospital.

Following consent of participation, the woman will then be assigned to either a control or experimental group. A separate research group, not directly affiliated with the project will perform the randomisation process. The research group will print x “control group” labels and x “experimental group,” in which each label is then sealed into an individual envelope. All envelopes will be numbered and issued in sequence. During the recruitment process, once the participant has given consent to partake in the trial, a member of the research team will select the envelope in sequence, which will then assign the participant to a group. This will prevent the person performing the randomisation from selecting another envelope if they are not happy with the group allocation. For this study, it will not be necessary to postpone diagnostic procedures or treatment, and participation will not influence normal treatment.

### *Surgical Intervention*

The same surgeons will operate on participants in both the control and experimental group. This will aim to exclude bias which may otherwise attribute findings to the surgeon operating. Surgery will be performed at Imperial Healthcare NHS Trusts and at the University College London Hospitals NHS Foundation Trust by an experienced clinician.

### *Data Collection*

The investigators will collect the following data: patient demographics including age, BMI, gravida, parity and gynaecological surgical history. Pre-operative data will include findings from the diagnostic transvaginal scan and measure of ovarian reserve: AMH and AFC. Intra-operative data will include transvaginal findings during surgery (in the experimental group only), such as cyst location and size or any new lesions noted. Residual ovarian volume post cystectomy will also be measured intraoperatively. Histology data will include the histological diagnosis of the ovarian cyst and volume of normal ovarian tissue excised during the cystectomy measured as per margins in mm. Outcomes following surgery including duration of surgery (mins), length of hospital stay (days) and post op complications will be recorded.

Post operatively, participants will return to clinic for follow up at 3 and 6 months post -surgery, whereby a blood test will be taken to assess ovarian reserve by measuring the AMH level. The outpatient gynaecology nurse in clinic or research staff will be responsible for taking the blood sample

and will only require one EDTA bottle (yellow top) to be filled (20-40mls). The blood samples will be processed by Imperial College Healthcare Trust laboratories or University College London Hospitals NHS Foundation Trust, depending on the site taken, and will be discarded as per local protocol once the AMH has been determined. There are no specific storage or transfer requirements outside of normal practice. Therefore, samples will be ‘podded’ to the labs once taken in the usual way. In addition, an ultrasound will be performed during the follow up appointment to measure AFC and assess volume of preserved ovarian tissue. Follow up appointments should take approximately 20 minutes. The two blood tests and two ultrasound scans carried out during the follow up process are considered standard clinical practice, and therefore not considered additional investigations for the purpose of this research study.

### 3.1 STUDY OUTCOME MEASURES

Primary: AMH and AFC measurements at 3 and 6 months post-surgery.

Secondary: Surgical outcomes including:

- Duration of surgical procedure (minutes),
- Duration of hospital stay (days)
- Presence of intra-operative cyst rupture or spillage (Yes/No)

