## 7.0 STATISTICS AND DATA ANALYSIS

A study by Kwon et al investigated the impact of laparoscopic ovarian cystectomy for benign cysts on post-operative ovarian reserve, as measured by follow up AMH levels taken 3 months after surgery. This particular study is considered to be most applicable for determining the power calculation of our proposed randomised controlled trial based on the following principles: pathology of the ovarian cysts were benign in nature and the sample size of the paper is one of the largest reported in the literature review.

From a sample size of 100 women, this paper deduced that AMH levels decreased on average 30.58% (+/-29.66%) between the pre-operative value to the level assessed 3 months following surgery. Specifically, the group of participants who underwent laparoscopic ovarian cystectomy for benign ovarian pathology had a mean (+/-SD) serum AMH of 1.59 (+/- 1.92)(ng/ml), which when converted to (pmol/L) is 3.57 (+/-4.31).

At present there are no reported studies assessing the change in AMH levels following ultrasound guided ovarian cystectomy. However, the investigators of this study have performed a small number of ultrasound-guided surgeries on 5 women, and therefore have a small data set, which can be considered a *pilot* study.

Amongst 5 women who have undergone ultrasound guided laparoscopic ovarian cystectomy, the mean difference (+/-SD) in AMH levels measured 3 months post operatively from pre-op levels is: 14.46 (+/- 21.02) pmol/L. This represents a substantial clinical difference according to previous research, and would imply women being less likely to experience fertility issues as they would be near the lower end of the normal range of AMH rather than in the lowest decile (ca. 0-4.5).

In order to calculate the sample size, the investigators have leveraged the pilot data to derive an estimate of the mean and standard deviation. From the literature, it can be assumed AMH is approximately log-normally distributed, as demonstrated from figure 1. Using this figure, the investigators have determined the normed (percentile) transformation of values from the pilot study.

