**(Table 1)**

Figure 1: Normed percentile transformation of AMH Values

[figure not shown]

Table 1: Estimated values of AMH differences based on normed percentile transformation

AMH Differences (pmol/L)		
	Treatment Group	Control Group
Mean	17.06	3.57
Standard Deviation (SD)	22.28	4.31
Coefficient of variation (CV) =(SD/Mean)	1.31	1.21
Number of participants	5	100

Using the pilot data, the investigators anticipate that 32 participants will be required to demonstrate a differential AMH level. (**Table 2**)

Table 2: Power Calculation

Sample Size Calculation		
	Treatment Group	Control Group
Mean (pilot)	17.06	3.57
Standard Deviation SD (pilot)	22.28	4.31
Standard Error (S.E)	6.18	1.08
Lower CI	4.70	1.42
Upper CI	29.42	5.73
Minimum (n)	11	11
Small sample margin	2	2
Attrition (assumed)	3	3
Total (n)	16	16

The minimum sample size is 11 participants. Considering the small size of the pilot and the very low risks thus far, the investigators include 2 more observations to boost power, and assume an attrition rate of approximately 25%. This leads to a total (n) of 16 participants per arm, with a power of 0.95 to detect a difference at the 5% level using a standard t-test on the log-transformed difference in means of AMH, the robust proxy for fertility. It will be necessary to perform an interim analysis given the low number of participants available for the power calculation.

With regards to further data analysis of the study, the investigators plan to use descriptive statistics (mean +/- standard deviation), two-sided tests, and Wilcoxon rank sum test to compare continuous variables in two groups. For more than two groups, the Kruskal-Wallis exact test will be used. For comparing a proportion with an expected value, a binomial exact test will be used. Results are considered significant at  $p<0.05$ . Analysis will be performed with SAS (version 9.2) and Statistical Package for Social Sciences for Windows (version 16). Statistical analysis will be performed under the supervision of [name].

Data and all appropriate documentation will be stored for a minimum of 10 years after the completion of the study, including the follow-up period.

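### AMH and AFC at 3 and 6 months are jointly primary, with no ranking, success rule or multiplicity adjustment, while the 5% level and 0.95 power are stated for one log-AMH test only

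*SAP*

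**What the plan says.** The Study Summary gives "Primary Outcome: Anti-Mullerian hormone (AMH) and Antral Follicle Count (AFC) measured at 3 and 6 months post-operatively", and section 3.1 repeats it: "Primary: AMH and AFC measurements at 3 and 6 months post-surgery". Section 1.3 says of efficacy: "This will be determined through assessment of post-operative AMH and AFC, which are both reliable measures of ovarian reserve". None of the three places puts one marker or one visit ahead of the other.

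Section 7.0 is narrower. The published cohort used for sizing assessed ovarian reserve "as measured by follow up AMH levels taken 3 months after surgery", and the pilot figure for five women is the mean difference "in AMH levels measured 3 months post operatively from pre-op levels is" reported in pmol/L. The sample size of 16 per arm is said to give "a power of 0.95 to detect a difference at the 5% level using a standard t-test on the log-transformed difference in means of AMH", with AMH described as "the robust proxy for fertility". AFC does not enter the sizing. The same section then lists, as further analysis, two-sided tests and the Wilcoxon rank sum test for continuous variables, and sets one general threshold of p<0.05.

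Section 7.0 also calls for an interim analysis because few participants underlie the power calculation. It gives no timing, endpoint, decision rule or error control.

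**The concern.** The plan defines four primary comparisons but states its error rate and power for one. Without a declared lead endpoint or success rule, the same data could be called positive or negative according to a rule chosen after the results are known. The trial is unblinded and small, so a rule fixed in advance matters more than usual.

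The consequence depends on which rule is applied:
- **Any one of the four counts:** the false-positive chance exceeds 5%.
- **AMH leads, but either visit may decide:** the chance still exceeds 5%, by less.
- **All four must succeed:** error is controlled, but 0.95 is not the power of the trial.

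The SAP selects none of these. Nor does it say whether the primary AMH comparison uses the t-test named for sizing or the Wilcoxon test named for continuous variables.

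**Working it through.** **1. Reproducing the plan's own figure.** Inputs from Table 1: mean (SD) 17.06 (22.28) for treatment and 3.57 (4.31) for control, in pmol/L. Log-normal conversion: σ² = ln(1 + CV²), μ = ln(mean) − σ²/2.
- Treatment: σ² = 0.995, μ = 2.339.
- Control: σ² = 0.899, μ = 0.823.
- Log difference = 2.339 − 0.823 = 1.516. Pooled SD = √((0.995 + 0.899)/2) = 0.973.
- n per arm = 2(1.960 + 1.645)² × 0.973² / 1.516² = 10.7, so 11. This matches the stated minimum. The exact t-test needs 12, with power 0.935 at 11.

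So the 5% level and 0.95 power describe one two-sided test of log AMH.

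**2. Any one of four counts (no interim).** If the four tests were independent, the chance of at least one false positive is 1 − 0.95⁴ = 0.185. For correlated tests, 1,000,000 null trials were simulated with four normal test statistics and a common correlation (an assumption):

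| Common correlation | At least one p<0.05 |
|---|---|
| 0 | 0.186 |
| 0.5 | 0.156 |
| 0.9 | 0.094 |
| 0.95 | 0.079 |

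If the two visits of one marker are allowed to correlate more strongly than the two markers do, the results stay within this range: 0.115 to 0.138 for within-marker 0.8 to 0.9 and between-marker 0.5 to 0.7, and about 0.167 for 0.5 and 0.3.

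**3. AMH only, at either visit.** Two tests: 0.078 at correlation 0.8 and 0.071 at 0.9.

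**4. All four must succeed.** The false-positive chance cannot exceed 5%, the level of each test. Power cannot be computed, because the SAP gives no AFC mean or SD.

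**5. Four primaries at 0.05/4 = 0.0125 each.** Family-wise error if independent: 1 − 0.9875⁴ = 0.049. Exact t-test power for AMH:

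| Inputs for the treatment arm | 16 per arm | 13 per arm | 11 per arm |
|---|---|---|---|
| Table 1 (17.06, SD 22.28) | 0.953 | 0.887 | 0.807 |
| Untransformed pilot, section 7.0 text (14.46, SD 21.02) | 0.82 | 0.70 | 0.60 |

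The second row uses the same conversion and the same control values (log difference 1.281, SD 1.009). AFC power is unknown in both rows.

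**6. Interim, counted separately.** For one AMH endpoint, with the timing assumed at half of the information, an unadjusted 0.05 look followed by 0.05 at the end gives 8.3% overall. With 0.001 at the interim and 0.05 at the end it is 5.0%.

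**The case against.** The strongest reply is that the plan already has a lead endpoint. Section 7.0 ties the level, the power and the t-test to AMH, draws its data from 3 months, and places the other tests under further analysis. The summary and sections 1.3 and 3.1 join AMH and AFC with an *and*; if that means both must succeed, there is no inflation.

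Much of this stands. A reader might infer that the trial runs at an inflated error rate, but the SAP never says that one result is enough, so the inflation is conditional on that rule. A reader might also settle on a narrow figure such as 11% to 14%. That rests on particular correlations that the SAP does not give, so only the wide range is defensible. Nor is it right that 5% and 0.95 can hold only if one AMH test decides: on Table 1's inputs, four tests at 0.0125 keep AMH power at 0.953 if all 16 per arm are evaluable.

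The interim should not be read as a planned efficacy look. Its stated reason points to checking planning assumptions, and the 8.3% needs a timing and an unadjusted test that the SAP does not state.

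What does not stand is the inference from sizing to declaration. A variable used for sizing is not thereby the primary outcome when three other places put AFC beside it. Even granting that AMH leads, nothing fixes the visit.

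**Conclusion.** The point holds as a failure to declare the lead endpoint, the deciding visit and the success rule. This is more than missing detail: the document itself fixes the outcomes, the threshold and the power, and these do not fit together.

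The size depends on the rule assumed: about 8% to 19% if any of four counts (common correlation 0.95 down to 0), about 7% to 8% if AMH at either visit counts (correlation 0.9 to 0.8), and no excess error but unknown power if all four must succeed. All the correlations are assumptions. It must be settled before analysis, because it decides what counts as a positive trial.

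One related conflict should be raised on its own. Section 7.0 gives a change from the pre-operative value for the pilot women but a level for control ("serum AMH of 1.59" ng/ml before conversion), while Table 1 heads both columns as differences.

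**What to change.** In the Study Summary, section 3.1 and section 7.0:
- Name AMH at 3 months as the single primary outcome, tested at two-sided 0.05 with the t-test on log AMH used for sizing. If change is meant, define it as the log ratio of post-operative to pre-operative AMH, since a negative difference has no logarithm.
- Make AMH at 6 months and AFC at 3 and 6 months secondary.
- Keep the Wilcoxon test as supportive for AMH.

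This costs wording in three places and no participants. The downside is that a result on AFC alone, or at 6 months alone, could not support the primary claim.

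A valid alternative is to keep four primaries at 0.0125 each. The cost is AMH power that falls below 0.95 once there is attrition (0.887 at 13 and 0.807 at 11 evaluable per arm on Table 1's inputs, lower on the untransformed pilot figures) and AFC power that cannot be stated.

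As a separate change, state that the interim checks planning assumptions only, with no between-arm efficacy test. If efficacy is to be examined, require p<0.001 at the interim and keep 0.05 at the end, for an overall error of about 5.0%.
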